Materials. All care partners will receive group-specific handbooks (Appendix A) ⁽⁵⁴⁾, *The FTD Roadmap*© (Appendix B) and access to the STELLA-FTD website with instructional resources and videos. The group-specific handbooks (either "Comet" or "Meteor") ⁽⁵⁴⁾ provide information on FTD and the weekly lessons. *The FTD Roadmap*©, designed and tested in the STELLA-FTD pilot, provides information on services that can support families throughout FTD disease progression. The materials will be sent to all care partners after they have completed the week 4 pre-intervention assessment. Care partners may keep their materials. Over the course of the study we will seek feedback from care partners about the utility of the materials (see **Measures**), and revise them for a future Stage 2 study⁽¹⁾.

The STELLA-FTD website will have two components: written instructional resources and recorded videos. Rehabilitation specialists and other professionals with experience working with FTD families will create one-page written educational documents and record 15-minute videos about how their specialty can help address current FTD symptoms and prepare for future needs. This information will align with the visual markers on *The FTD Roadmap*®. Care partners will access the videos on the private STELLA-FTD website with their user ID and password and can watch the videos whenever they need to, even after they have completed STELLA-FTD. We will monitor engagement with the website, in which metrics will provide robust objective data, indicating how often participants log in and view the resources and videos.

The Intervention: How the study includes the hypothesized mechanism of action. We hypothesize that STELLA-FTD's mechanism of action involves training in the ABC analytic approach (the behavior change technique). The training increases care partner self-efficacy (the intervention target and mediating variable), that results in decreased burden (the outcome variable) ⁽⁵⁵⁾. Here we describe the training method.

The STELLA-FTD intervention is delivered over 8 weeks in 1-hour “live” video-based group sessions led by two guides. There will be two intervention groups, the control group (“Comet”) and the test group, (“Meteor”) (Figure 2). There will be up to 8 care partners per group, which allows for the development of mutual trust and commitment ⁽⁵⁶⁾.

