Assessments	Pre-Intervention Assessment	1 week prior to STELLA-FTD start
STELLA-FTD Intervention	Meet with Faculty and Guest Speakers for 8 weekly, 1-hour, sessions	1 week after pre-intervention assessment
Assessment	Mid-intervention Assessment	4 weeks after start of STELLA-FTD sessions
Assessment	Post Assessment 1	Within one week of completion of STELLA-FTD
Assessment	Post-Assessment 2	2 months after end of STELLA-FTD
Assessment	Post-Assessment 3	6 months after end of STELLA-FTD
Weekly Orbit Surveys: Distributed weekly		
Orbit surveys start after enrollment and continue until all surveys are completed		

Measures (Table 3). The primary outcome variable, burden, will be assessed with the 24-item RMBPC (2), which measures the frequency of care recipient behavioral symptoms and care partner reactions to these behaviors. The RMBPC was chosen because it aligns with our theoretical foundation that assumes burden is a result of care partner reactions to behavioral symptoms. The RMBPC has been used in Teri's work (30) and our telehealth

studies, (29, 31, 33, 34) including the STELLA-FTD pilot, allowing for comparison across studies.

Self-efficacy, the mediating variable, will be assessed using Fortinsky's measurement of family care partner self-efficacy for managing dementia (3). We considered the other measures, but Fortinsky's assesses the targets in STELLA-FTD: behavior symptom management and service use.

We will measure care partner preparedness for current and future challenges (63) and personality type to test the effect of a group-based intervention (64).

For care partners in STELLA-FTD+ABC, we will assess the results of the care partners' personalized ABC plans prior to and after the 8-week intervention by collecting data on the frequency of their identified behaviors, and their reactions to them, on their Personalized Target Behavior Survey (29, 30). We will collect data on number of ABC plans each care partner writes on the Orbit weekly survey, weeks 4-36.

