H1: Upon completion of the STELLA-FTD 8-week intervention, care partners in the test group will have significantly lower (better) burden scores than those in the control group. For H1, we will employ a mixed effects model to analyze whether the change in reactivity on the RMBPC (2) differs across groups (test vs. control) over the intervention period. Two fixed effects will be included in the model: 1) Group effect will be included as a dichotomous categorical variable (test vs. control); 2) Time effect will be included as a continuous variable. The interaction between group and time (group x time) will also be included. Random intercepts will be incorporated for subject specificity in the model to account for clustering effect within subject over time. We will perform a hypothesis test for the coefficient of the interaction term (group x time) to assess the difference in change on primary outcome in the intervention group as compared to control group, over time. We will extend the model to include diagnosis type (e.g., PPA, bv-FTD), frequency of behavioral symptoms as measured on the RMBPC (2), socio-demographic covariates (e.g. sex, age, sex, education) and external support group use. Results will be considered significant at $\alpha = 0.05$, with two-sided test. Similar analyses will occur at Week 20 and 36.

Aim 2. Test the mechanism of action of STELLA-FTD by isolating the ABC training component (the behavior change technique) and determining its relationship to self-efficacy (the intervention target) and burden (the primary outcome) (Figure A).

The statistical analyses for Aim 2 will be carried out in three steps to investigate the mediated effect of self-efficacy ⁽³⁾ on the association between intervention and primary outcome, the RMBPC ⁽²⁾ reactivity score.

H2: Care partners who receive STELLA-FTD with ABC training (the test group) will have significantly higher self-efficacy scores ⁽³⁾ than the control group. To test H2 in the first step, we will employ a similar mixed effect model as H1. The mixed effect model analyses will be performed on total self-efficacy score as the outcome. A hypothesis test for the coefficient of the interaction term (group x time) will be performed to assess the difference in change on self-efficacy score in the test group as compared to control group, over time.

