H3: Care partners with higher self-efficacy will have lower burden scores. In the second step to test for H3, we will construct a mixed effect model on the RMBPC ⁽²⁾ reactivity score as the outcome. Total self-efficacy score ⁽³⁾ will be included as a continuous independent variable; time will be included as a continuous variable. The interaction between total self-efficacy score and time (self-efficacy score x time) will also be included. Random intercepts will be incorporated for subject specificity in the model to account for clustering effect within subject over time. A hypothesis test for the coefficient of the interaction term (self-efficacy score x time) will be performed to assess the relationship between change on primary outcome (RMBPC reactivity score ⁽²⁾) and total self-efficacy score ⁽³⁾, over time.

H4: Self-efficacy will partially mediate the relationship between ABC training and burden. In the third step, a mixed effect model on RMBPC reactivity score ⁽²⁾ will be constructed based on the model in H1. We will extend the established model in H1 to include total self-efficacy score as a continuous covariate and the interaction term between total self-efficacy score and time (self-efficacy score x time) will also be included. We expect the interaction term coefficient (group x time) in model for H1 will be significant, and the coefficient of the interaction term between group and time (group x time) will be attenuated and may become non-significant after extending the model to add total self-efficacy score as a covariate and the interaction between total self-efficacy score and time (total self-efficacy score x time). This will indicate that the self-efficacy has a mediated effect on the association between the intervention and change in the primary outcome (RMBPC reactivity score ⁽²⁾) as compared to the control group. We will also extend these models to include diagnosis, frequency of behavioral symptoms as measured on the RMBPC ⁽²⁾, socio-demographic covariates and preparedness (78). All of results above will be considered significant at $\alpha = 0.05$, with two-sided tests.

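### Aim 2: H3 is worded as a level association but its only named test is self-efficacy x time, and H4 reads attenuation as mediation with no indirect effect, interval or size that counts

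*Combined protocol and SAP*

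**What the plan says.** Sections 2 and 8 both state "H3: Care partners with higher self-efficacy will have lower burden scores". Section 6, on the hypothesised mechanism, describes the same path: "The training increases care partner self-efficacy (the intervention target and mediating variable), that results in decreased burden".

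The H3 model in section 8 has RMBPC reactivity as outcome, with total self-efficacy, continuous time, their product and a random intercept. One test is named: "A hypothesis test for the coefficient of the interaction term (self-efficacy score x time) will be performed to assess the relationship", and the sentence goes on to say that this is the relationship between change in reactivity and total self-efficacy over time. No test of self-efficacy's own coefficient is named. No coding of time is given, and the plan does not say whether self-efficacy is updated at each visit or fixed at one.

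For H4, the H1 model is extended with self-efficacy and its product with time. The group x time coefficient "will be attenuated and may become non-significant after extending the model to add total self-efficacy score as a covariate", together with that product. The plan then concludes: "This will indicate that the self-efficacy has a mediated effect on the association between the intervention and change in the primary outcome". Tests are two-sided at 0.05. Aim 2 is introduced as three steps (H2, H3, H4), without saying that one step depends on another.

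On visits, H1 is to "analyze whether the change in reactivity on the RMBPC (2) differs across groups (test vs. control) over the intervention period", and "Similar analyses will occur at Week 20 and 36". Table 3 lists only the RMBPC at the week 8 mid-intervention assessment. Both scores are listed at weeks 1 and 4 and at all three post assessments.

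**The concern.** A product with time asks whether the link between self-efficacy and burden strengthens or weakens across visits. H3 asks whether there is a link. A link that is present and stable makes H3 true and the product zero.

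Under H4, adding almost any covariate moves a coefficient a little, up or down. A criterion that asks only for the direction of that movement has no controlled error rate. The 0.05 level applies to each coefficient, not to the difference between two models. If the H1 model uses week 8 and the H4 model cannot, part of any shift may also come from different data.

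At stake is the mechanism claim, which section 4 gives as a reason for having two groups. A true but stable H3 would usually be reported as unsupported, while trivial shrinkage would fit the H4 wording for mediation.

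**Working it through.** **Inputs.** The plan gives no figure for H3 or H4. Its sample size (section 4) supplies the scale: effect 0.3, three measures, ICC ρ of 0.5 to 0.6, 80% power, alpha 0.05. It reproduces as n = 2(1.960 + 0.842)² × [(1 + 2ρ)/3] / 0.3²:
- ρ = 0.5: 15.70 × 0.6667 / 0.09 = 116.3, so 117 per group.
- ρ = 0.6: 15.70 × 0.7333 / 0.09 = 127.9, so 128 per group.

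Visit times: Table 2 puts Post Assessment 2 "2 months after end of STELLA-FTD" and Post Assessment 3 six months after. With weeks 20 and 36 from section 8, 20 − 8 = 36 − 24 = 12, so Post Assessment 1 falls at about week 12.

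**Assumptions not in the documents.** 128 per arm, ICC 0.55, complete data, no clustering by session group, standardised scores, time-varying self-efficacy. S = subject + noise + a·group·post; Y = subject + noise − b·S − c·group·post. Random-intercept models, 2,000–3,000 trials per setting unless stated.

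**H3, algebra.** With Y = β0 + β1·S + β2·t + β3·S·t + u + e, the slope of burden on self-efficacy at time t is β1 + β3·t. H3 as worded says this slope is negative. The named test is of β3 = 0, which is true for any constant slope, however steep.

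**H3, simulation.** Rejection rates in %, for weeks 4/12, then 1/4/12, then 1/4/12/20/36. The level coefficient is that of self-efficacy in a model with group, time and group x time but no self-efficacy x time. The constant-slope rows have no arm effects.

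| Slope (SD) | Named test | Level coefficient |
|---|---|---|
| constant −0.15 | 5.4, 4.5, 4.9 | 91.9, 98.9, 100 |
| constant −0.3 | 4.7, 5.2, 5.4 | 100 |
| constant −0.8 | 5.1, 4.8, 4.8 | 100 |
| −0.3 before, −0.35 after training | 16.5, 22.0, 18.4 | 100 |
| 0 before, −0.2 after | 90.8, 96.8, 97.6 | 60.8, 46.1, 99.5 |
| −0.1 before, −0.4 after | 99.6–100 | not tabulated |

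With arm effects added (a = 0.32, c = 0.2, constant −0.3) the named test gives 5.6, 6.6 and 4.3. A separate rerun of 1,000 trials per setting gave 4–6% for the named test under constant slopes, against 91–100% for the level coefficient.

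If the product is kept, β1 refers to time zero, so coding matters. At a constant −0.15 on weeks 4/12, β1 rejects in 47.0% with uncentred weeks and 78.3% centred at week 12, against 91.9% without the product.

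**H4, third step alone.** Share of trials with a significant H1 in which group x time shrinks although there is no mediation (c = 0.3, same visits in both models):

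| Setting | Weeks 4/12 | Weeks 1/4/12 |
|---|---|---|
| a = 0, b = 0 | 48.8% | 50.8% |
| a = 0, b = 0.3 | 58.1% | 54.0% |
| a = 0.32, b = 0 | 52.0% | 52.5% |
| a = 0.5, b = 0 | 51.9% | 54.2% |

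Median shrinkage among those trials is 1–7%; the coefficient also becomes non-significant in 1–7%. With true partial mediation it shrinks in 99.8–100%. Direction alone is sensitive but not specific.

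**H4, read as a sequence** (rerun of 1,000 trials per setting, given a significant H1):

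| Required | No arm effect on self-efficacy | No self-efficacy effect on burden |
|---|---|---|
| Attenuation only | 49–59% (both columns) | |
| Plus H2 significant | 2–3% | 40–52% |
| Plus H2 and H3 significant | 0–9% (both columns) | |

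Requiring all three detects only about 6% of true partial mediation with a constant link, because the H3 test seldom rejects.

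**The case against.** **The plan means change.** The H3 sentence says so, and H1 and H2 are also worded as levels and tested through a time interaction. It stands that the plan says what the product is for. But randomised groups are expected to start alike, so for H1 and H2 a later difference and a differential change come to much the same thing. Self-efficacy may be linked to burden from the first visit, and then the two questions part. Either the hypothesis or the test has to move.

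**A fixed score.** If self-efficacy were entered as a single early score, the product would test whether change in burden depends on it. That reading is open, but a pre-intervention score cannot carry an effect of training, and H3 as worded would still be untested.

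**The main effect is in the model.** It is, so the link can be estimated. No test of it is named, and its meaning depends on an unstated time origin.

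**The named test can work.** This stands: it rejects in 91–98% of trials when a link of −0.2 emerges only after training. A reader might infer that the plan cannot detect H3 at all. The documents give no trajectory, so the failure is limited to stable or nearly stable links.

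**H4 is the last of three steps.** This stands too. A reader might infer that the plan would falsely claim mediation in about half of all trials. The text does not support that: the figure is for the third step alone, given a significant H1, and H2 and H3 come before it. Equally, the plan does not say that they must succeed first.

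**Covariates.** The planned extensions (diagnosis, symptom frequency, socio-demographics, preparedness) can reduce measured confounding. They do not supply an indirect effect or a criterion.

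**Conclusion.** The point holds and should be fixed before analysis. The H3 mismatch rests on the text and on algebra; its size rests on a time-varying score and a stable link, under which the named test rejects at about its alpha whatever the strength of the link. For H4, the absence of an indirect effect, an interval or a minimum attenuation is a matter of text. The resulting rate of false mediation claims depends on gating the plan leaves open: about half for the third step alone, 40–52% if only H2 is also required and self-efficacy has no effect on burden, and 0–9% if H3 is required as well, at the price of detecting almost no mediation through a stable link.

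The H1 and H4 models may use different visits because self-efficacy is not listed at week 8. A reader might infer a known bias from this. None is shown: size and direction depend on the visits used and the trajectory, and all simulations here used common visits.

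Path sizes are assumptions. H1, H2 and the sample size are unaffected.

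**What to change.** 1. **H3.** Make the primary test the time-varying self-efficacy coefficient in a model with group, time and group x time and without self-efficacy x time. Name the visits. If weeks 20 and 36 are included, enter visit as a category: with arm effects but no link, linear time over five visits gave 8.7–9.0% false rejections, against 5.0% with categories. Keep the product as a secondary test of whether the link changes.
2. **H4.** Replace the attenuation criterion with a pre-specified indirect effect and 95% CI: the arm effect on Post Assessment 1 self-efficacy adjusted for its pre-intervention score, times the effect of that self-efficacy on reactivity adjusted for arm and both pre-intervention scores. Name the primary burden visit in advance, and report a later visit as well so that the mediator precedes the outcome. Simulated at Post Assessment 1 without confounding, this gave 0–5.8% false claims and 86–100% power.
3. **Rows.** Fit any models being compared to the same participants and visits.
4. **Confounding.** State the no-unmeasured-confounding assumption and add a sensitivity analysis. The indirect effect does not remove confounding: with no true effect of self-efficacy on burden and an assumed residual correlation of −0.1 or −0.2, it gives false claims in 28–36% or 76–89% of trials. Attenuation fares no better, occurring in 93–97% or over 99% of trials with a significant H1.

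**Cost.** SAP wording and modest extra analysis; Table 3 already schedules both scores at the visits needed. The H3 choice has a downside if the link appears only after training (0 to −0.2): on weeks 4/12 and 1/4/12 it has 61% and 46% power, against 91% and 97% for the product and 95% and 96% for a coefficient centred at week 12. For a constant −0.15 it has 92% and 99%, against 78% and 84% for the centred coefficient.

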In Teri et al. ⁽³⁰⁾ the differences in RMBPC reactivity scores ⁽²⁾ between baseline and post-intervention visit were -1.6(SD=7.6) with an effect size of 0.21 in care partners in the control group (routine medical care), and -5.8(SD=9.8) with an effect size of 0.59 in care partners in the intervention group (the ABC group). The effect size of difference in change in RMBPC ⁽²⁾ reactivity score between the two groups was 0.38. Based on this study, we conservatively determined the sample size calculation with an effect size of difference in pre-post intervention change as 0.3. To achieve at least 80% power to detect such a difference in a study design with three repeated measurements and an Intra-Class Correlation (ICC) =0.5 to 0.6 in compound symmetry covariance structure, we need at least 117 to 128 subjects/each group, for alpha = 0.05.

We anticipate an increase in power due to our conservative approach, e.g., based on three time repeated measures instead of 6 time points (Figure 2) and smaller effect size between intervention

and control groups on the RMBPC (compared to 0.59 Teri et al.)⁽³⁰⁾. We will use this increase in power to compensate for the complexity of the proposed model when adjusting covariates are taken into consideration. For self-efficacy, based on estimates from the STELLA-FTD pilot, group sample sizes of 128 will achieve 80% power to detect a difference of 0.32 at alpha level of 0.05, which is reasonable given pilot data trends⁽⁴²⁾.

In determining the sample size, we took attrition into account. Based on our experience⁽²⁹⁾, it is likely that up to 15% of the sample will withdraw due to schedule demands, illness and death, thus we will over-recruit to enroll 300 care partners.

5) Study Population

a) Number of Subjects

Participants. Informed by our power analysis, we will enroll a total sample of 600 participants: 300 family care partners and their 300 care recipients with FTD. For our study “family care partner” includes any person who is considered “family” to the person with FTD, such as direct relations, fictive kin, close friends and neighbors. “Care recipient” is defined as an individual with an FTD diagnosis: bv-FTD, PPA, progressive supranuclear palsy (PSP), corticobasal degeneration (CBD), or FTD with motor neuron disease⁽⁴³⁾.

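### H4 adds the raw repeated self-efficacy score and reads any attenuation as mediation; if training raises self-efficacy and confident care partners are less reactive, attenuation will usually appear without mediation

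*Combined protocol and SAP*

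**What the plan says.** Section 8) Data Analysis, Aim 2, sets out three steps. H2 repeats the H1 random-intercept model with self-efficacy as the outcome. H3 models RMBPC reactivity on self-efficacy: the total score "will be included as a continuous independent variable; time will be included as a continuous variable", and the test is on score x time. H4 returns to the H1 model: "We will extend the established model in H1 to include total self-efficacy score as a continuous covariate", again with score x time. The plan expects group x time to be significant in H1 and then to shrink, with loss of significance possible but not required. It concludes: "This will indicate that the self-efficacy has a mediated effect on the association between the intervention and change in the primary outcome".

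The significance rule for Aim 2 is: "All of results above will be considered significant at $\alpha = 0.05$, with two-sided tests". The section gives no minimum shrinkage and no test or interval for an indirect effect. It does not say that each step must succeed before the next, and it mentions no centring, baseline term or lag for self-efficacy.

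Table 3 schedules self-efficacy at weeks 1 and 4 and at the three post assessments. The week 8 assessment lists the RMBPC only.

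**The concern.** Two different associations can link self-efficacy with burden. One lies between people: care partners who are generally more confident may be generally less reactive. The other lies within a person: when a care partner's confidence rises, her reactivity may fall. Mediation of a training effect concerns only the second.

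A raw repeated score in a random-intercept model has one coefficient that averages the two. If training raises self-efficacy, the between-person part of that coefficient is multiplied by the rise and taken out of group x time. The training effect then looks partly explained, even when changing self-efficacy does nothing to burden.

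The conditions for this are close to what the sponsor expects. H2 says that training raises self-efficacy, and H3 as worded covers a between-person link. Mechanism of action is a Specific Aim and the stated reason for the dose-matched control, so a positive H4 that cannot be interpreted would be a real loss.

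**Working it through.** **1. The plan's own figure.** Section 4, Sample size calculation, says "we conservatively determined the sample size calculation with an effect size of difference in pre-post intervention change as 0.3", with "three repeated measurements and an Intra-Class Correlation (ICC) =0.5 to 0.6 in compound symmetry covariance structure", and concludes "we need at least 117 to 128 subjects/each group, for alpha = 0.05". For a time-averaged comparison, n per group = 2(1.96 + 0.842)² x [1 + (m-1)ICC]/m / d², with m = 3 and d = 0.3.
- ICC 0.5: 15.70 x 0.667/0.09 = 116.3, so 117.
- ICC 0.6: 15.70 x 0.733/0.09 = 127.9, so 128.

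Both match, so these inputs are a fair base for simulation.

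**2. Inputs.**
- From the plan: 128 per arm, a 0.30 SD effect on burden, ICC 0.5 and 0.6, random intercepts, two-sided 0.05.
- From the plan, read in SD units by assumption: a 0.32 rise in self-efficacy.
- Assumed: between-person correlation r from 0 to -0.5.
- Set to zero: the within-person effect of self-efficacy on burden, so there is no mediation.
- Visits: weeks 4/12 and 1/4/12, 2,000 runs per setting. The Monte Carlo standard error is at most √(0.25/2000) = 1.1 percentage points.

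**3. Mechanism.** The raw coefficient is roughly b = w·b_between + (1-w)·b_within, with w between 0 and 1. With b_within = 0 and b_between = r, the false mediated share is about 0.32·w·|r|/0.30 = 1.067·w·|r|. It grows in proportion to r and vanishes if r = 0 or if training does not move self-efficacy.

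**4. Results with the raw score and no true mediation.**

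| r | Any shrinkage, given significant H1 | Significance also lost, given significant H1 | Mean false mediated share |
|---|---|---|---|
| 0 | about 50% | 3-5% | about 0 |
| -0.2 | 84-89% | 8-12% | 5.8-8.1% |
| -0.35 | 93-98% | 14-21% | 10.0-14.5% |
| -0.5 | 98-99% | 19-30% | 14.9-21.3% |

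Against step 3, these shares imply w = 0.27-0.38, 0.27-0.39 and 0.28-0.40 at the three correlations (for example 0.058/(1.067 x 0.2) = 0.27). The weight is stable, as the formula requires. Further runs that included all five self-efficacy occasions widen the mean share to about 4-22%.

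**5. Other readings of the rule.**
- H1, H2 and H3 (score x time) must all be significant as well: 2-5% of trials.
- Training does not move self-efficacy: shrinkage in about 50% given a significant H1, mean share about 0.

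**6. Would a test on the raw score cure it?** Requiring H1, H2 and a significant raw self-efficacy coefficient still gives false mediation in 12-25%, 27-58% and 43-72% of trials at r = -0.2, -0.35 and -0.5. A joint test of the two paths, without H1 and with score x time left out, is falsely positive in about 60% at r = -0.3. With score x time included and time in raw study weeks, it is 24-45%. The plan specifies none of these tests. They show only that adding a test to the raw score is not a remedy.

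**7. After splitting the score.**
- Mean false share: about 0-0.6% (up to about 1.6% over the wider visit sets).
- Any shrinkage, given a significant H1: still about half of trials, and up to about two-thirds in the wider runs.
- H1, training path and within-person path all significant: 1-2% false mediation, or 3-6% over five occasions.
- One true-mediation setting (half the effect mediated: 0.32 x 0.47 = 0.15 of 0.30; weeks 1/4/12, ICC 0.55, r = -0.35): the split joint test detects it in 65% of trials, as does the raw-score version. The split recovers a 50% share.

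**8. H3 as a safeguard.** Its test, score x time, was significant in about 6% of runs both without mediation and in the true-mediation setting. It does not tell the two apart.

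**The case against.** A reader might infer that H4 will usually report mediation when there is none, or that a false positive is close to guaranteed. The documents do not support that. They give no between-person correlation. The high frequencies also need training to move self-efficacy and the most literal rule, in which any shrinkage counts. The plan speaks of three steps, each at 0.05. If all three must be significant, the false rate is 2-5%. If significance must be lost, it is 8-30% given a significant H1 (6-33% over the wider runs). This stands, and the point is conditional for that reason. The plan imposes neither requirement, however, so the rule itself is unclear.

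Nor should the figure of about 60% be read as the plan's error rate, because the plan contains no such test.

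The raw score is also not the only cause. With a properly split score the any-shrinkage rule remains close to a coin flip, so the missing indirect-effect test matters as much.

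Three smaller points stand:
- H3 as worded covers the between-person association, so that coefficient is of interest there.
- The planned covariates (diagnosis, behaviour frequency, socio-demographics, preparedness) may absorb part of the between-person link. They were not simulated, and they do not separate the two associations.
- The text does not expressly say that the visit-level score is used. The repeated schedule makes it the natural reading, and a baseline score could not carry an effect of training.

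**Conclusion.** The point holds in conditional form. As written, H4 uses a coefficient that blends between-person and within-person association, and it infers mediation from shrinkage alone. If training raises self-efficacy by about 0.32 SD and the between-person correlation is about -0.2 or stronger, shrinkage appears without mediation in about 84-99% of trials with a significant H1. The mean false mediated share is about 4-22% for correlations of -0.2 to -0.5. Near zero correlation the any-shrinkage rule is about a coin flip and the mean share is about nil.

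The size rests on the assumed correlation, on reading 0.32 in SD units, and on simulations without covariates, dropout patterns, measurement error or same-occasion confounding.

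This should be fixed. It affects the interpretation of Aim 2. It does not touch H1, the primary comparison.

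**What to change.** - **Split the score.** In H3 and H4, replace the total score by the care partner's own mean self-efficacy and the visit deviation from that mean.
- **Settle score x time.** State how it is carried over, for example as deviation x time with time centred, or dropped.
- **H3.** Report both coefficients, labelled as between-person and within-person.
- **H4.** Replace the shrinkage criterion by a pre-specified indirect effect, the training effect on self-efficacy times the within-person coefficient, with a confidence interval. State whether H1 and H2 must be significant first.
- **Limitation.** Say that both scales are self-reported at the same occasion, so same-occasion confounding survives the split.

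The cost is SAP wording and two derived variables, with no new data. The downside is a larger standard error for the within-person coefficient. In the one true-mediation setting examined, detection was not reduced (65% with either score), but that is a single setting.

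### H4 takes attenuation of the group x time coefficient as evidence of mediation without requiring that ABC training changed self-efficacy (H2)

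*Combined protocol and SAP*

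**What the plan says.** The protocol names one primary outcome, in Section 6 under Measures: "The primary outcome variable, burden, will be assessed with the 24-item RMBPC (2"). The reactivity score is the part used. Self-efficacy is the mediating variable and intervention target.

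Section 8 sets the level for H1 ("Results will be considered significant at $\alpha = 0.05$, with two-sided test") and then introduces Aim 2: "The statistical analyses for Aim 2 will be carried out in three steps to investigate the mediated effect of self-efficacy". The steps are:

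- **H2.** The test group "will have significantly higher self-efficacy scores" than the control group. The test is the group x time coefficient on total self-efficacy, "to assess the difference in change on self-efficacy score in the test group as compared to control group, over time".
- **H3.** Reactivity is modelled on self-efficacy, time and their interaction. The model is described without a group term.
- **H4.** Self-efficacy and self-efficacy x time are added to the H1 model. The plan states: "We expect the interaction term coefficient (group x time) in model for H1 will be significant". It goes on to expect that this coefficient will shrink and may lose significance, and says that this will indicate mediation.

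The closing sentence on level is "All of results above will be considered significant at" 0.05, two-sided. No step is made conditional on an earlier one. For H4, the plan sets no minimum amount of attenuation. Only the Orbit survey analyses are called exploratory.

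**The concern.** A mediation claim has two links: ABC training must move self-efficacy, and self-efficacy must bear on burden. The H4 rule looks only at whether the treatment coefficient gets smaller when self-efficacy enters the model. That can happen when the first link is absent, because a chance imbalance between the groups in self-efficacy change is enough. H3 cannot supply the missing link, since it is an association between self-efficacy and burden and not a randomised comparison.

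The mechanism of action is the whole of Aim 2 and the reason given in Section 4 for the dose-matched control group. A rule that can declare a mechanism when ABC training left self-efficacy unchanged could carry the wrong active ingredient into the Stage 2 trial for which Aim 3 prepares.

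**Working it through.** **1. The plan's level and sample size.** Section 4 gives effect size 0.3, three measurements, ICC 0.5 to 0.6, 80% power, alpha 0.05, and 117 to 128 per group. With the time-averaged difference under compound symmetry:

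n per group = 2 x (1.96 + 0.842)^2 / 0.3^2 x (1 + 2 x ICC)/3

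- ICC 0.5: 174.4 x 0.667 = 116.3, rounded up to 117.
- ICC 0.6: 174.4 x 0.733 = 127.9, rounded up to 128.

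The stated figures reproduce, and they confirm that 0.05 is two-sided. One-sided 0.05 would give 92 and 101.

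**2. Why attenuation is close to a coin toss when H2 is null.** Let c be the H1 group x time coefficient, c' the same coefficient after self-efficacy is added, a the group x time effect on self-efficacy, and b the slope of burden on self-efficacy. To a good approximation c - c' = a x b.

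Suppose ABC training works on burden (c negative), higher self-efficacy goes with lower burden (b negative), and ABC training does nothing to self-efficacy (true a = 0). The estimate of a is then positive in half of trials. In that half, a x b has the same sign as c, so c' is smaller in size than c. The rule is therefore met by chance about 50% of the time. Restricting to trials with a significant H1 pushes this up somewhat, because a chance gain in self-efficacy also makes the estimate of c look larger.

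**3. Simulation of the rule.** Assumptions: a real burden effect, no effect on self-efficacy, and self-efficacy/burden slopes of 0.3 to 0.5 SD. The slopes are not in the documents.

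| Condition for reading mediation | Met, among trials with significant H1 |
|---|---|
| Attenuation only (as written) | about 50-56% |
| Attenuation and significant H2 | about 2-3% |

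The second row agrees with simple arithmetic: a null H2 is significant with probability 0.05, and half of those results lie in the attenuating direction, so 0.05 / 2 = 0.025. The first row can move by a few points with the assumed burden effect and the visits analysed; its order of magnitude does not.

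**4. Context: H1 and H2 as a pair.** If ABC training changes neither burden nor self-efficacy, the chance of at least one two-sided significant result is 1 - 0.95^2 = 9.75% for independent tests. It is 9.1% at an assumed correlation of 0.5 and 8.4% at 0.7. The chance of a false result favouring ABC on either test is 1 - 0.975^2 = 4.9% if independent and 4.5% at a correlation of 0.5. The documents give no correlation.

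**The case against.** The strongest defence is that the three steps form one chain. H2 is called the first step, all three serve a single stated purpose, and the H4 sentence describes a significant H1 that then shrinks. A sensible analyst would not claim mediation after a null H2. That is probably the intent, but the text does not say so. H2 is tested and reported separately, and the sentence that defines evidence of mediation does not mention it.

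A second defence is that nobody would call a trivial reduction mediation. That has some force: the 50-56% counts any reduction, and a reader who insisted that the coefficient lose significance would find the rule met much less often. But the plan says only that significance may be lost, and it sets no threshold.

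The other side is also right about a wider criticism. A reader might infer that, because H1, H2 and H3 are each tested at 0.05, an ineffective ABC component has a 12-14% chance of some false positive, or that the mechanism conclusion lacks its stated error rate. The documents do not support either. An ineffective ABC component does not make the H3 null true: self-efficacy can be related to the burden trend with no ABC effect, and a significant H3 is then a true finding. The plan states 0.05 per test and no family-wise rate, and H1 and H2 each keep 5%. Nor does anything in the plan make a significant H2 count as trial success.

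Nor is there a compelling case that H2 must be gated on H1. One primary outcome is named, self-efficacy comes before burden in the plan's own model (Section 6), and H2 has its own power statement (Section 4).

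**Conclusion.** The point holds for the interpretation of H4. As written, the rule can declare a mechanism that does not exist. When ABC training affects burden but not self-efficacy, it does so in about 50-56% of trials with a significant H1, against about 2-3% if a significant H2 is also required. These figures rest on assumed slopes of 0.3-0.5 SD and on counting any attenuation, which is what the text allows. The near-50% value does not depend much on the slopes, because it follows from the sign of a chance imbalance.

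The point does not reach the H1 test, whose error rate stays at 5%. The figure of about 9% for H1 or H2 (4.5-4.9% in favour of ABC) is context and not a defect in the primary analysis.

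**What to change.** In Section 8, Aim 2, state that:

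- H3 and H4 are supportive analyses;
- they are interpreted as mediation only if the end-of-intervention H1 test and the H2 test are both significant at two-sided 0.05;
- otherwise the H3 and H4 estimates are reported with 95% confidence intervals and labelled exploratory.

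The H1 condition only makes binding what the plan already expects. The H2 condition is the new element. Whether to claim H2 itself only after a significant H1 is optional.

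The cost is a few sentences, with no new data or participants and no change to the H1 or H2 tests. The downside is that no mediation claim is made when either test misses. If H1 and H2 each had 80% power with an assumed correlation of 0.5, both would be significant in about 69% of trials, against 80% for H1 alone. All estimates would still be reported.
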